**Specific Aim 1:** To test whether the eTEST intervention results in higher rates of (a) initial and follow-up HIV testing, and (b) receipt of additional prevention services after testing (e.g., STI testing, risk reduction counseling, safer sex supplies) compared with standard HBST and reminders for clinic-based testing among MSM in three US regions with large AA and H/L MSM populations. As an exploratory aim, we will also examine whether receiving HBST helps detect more infections during the study period and reduces the time to diagnosis among those receiving reactive results, compared with clinic-based testing alone.

**Specific Aim 2:** To test whether providing focused information/counseling about PrEP during eTEST contacts results in more participants (a) consulting with medical providers about PrEP and (b) initiating PrEP. We will define a PrEP care continuum, including the number of MSM who meet clinical indications for PrEP, the number who are interested in and are linked to care, the number who are prescribed PrEP, and the number who initiate PrEP in each condition.

**Specific Aim 3:** To assess the cost-effectiveness of the eTEST system for improving rates of HIV testing compared with clinic-based testing alone. We will use mathematical models to estimate whether the eTEST system (and HBST) can be cost effective under various scenarios (e.g., testing intervals).

The proposed research will provide a robust test of the feasibility, efficacy, and value of home-based testing programs with post-test follow-up in communities with large populations of AA and H/L MSM that are highly affected by HIV. It is also among the first studies in the US to leverage HBST to engage difficult-to-reach populations in care. Results can also inform efforts to seek high-risk MSM and engage them in PrEP services.

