**Overview of Research.** Given these issues, the proposed research involves conducting a fully-powered efficacy test of HBST and the eTEST system's effects on rates of any/repeat HIV testing, use of other prevention services (e.g., STI testing, HIV risk reduction counseling), and PrEP linkage/initiation, compared with "standard" HBST and reminders for clinic-based testing, among high-risk MSM in three regions in the US: The Deep South (Jackson, MS), West Coast (Los Angeles), and Northeast (Providence/Boston). High-risk MSM ( $N=2000$ ,  $N=666$  per metro) who have not tested in the last year will be recruited online using an interactive web application. Participants will be randomly assigned to one of three arms that involve receiving one of the following at baseline, 3, 6, and 9 months: (1) HBST with phone follow-up (eTEST condition), (2) standard HBST (no follow-up), or (3) reminders for clinic-based testing only (control). Only enhanced eTest participants will be provided with the eTEST app, which will monitor the status of HBST kits and facilitate phone follow-up. Control participants will receive text messages at quarterly intervals, reminding participants to get tested in a clinic. Participants in the standard HBST condition will receive their HBST in the mail when it is time for their quarterly tests. All study participants will have access to information that may be generally helpful (e.g., information about HIV, testing, and a testing clinic locator) and are already publicly available. Throughout the study, all participants will complete online questionnaires assessing key outcomes each quarter, which will be confirmed by reviewing clinical records in each local area when possible. Analyses will assess eTEST's efficacy within and across regions, as well as the cost-effectiveness of these strategies compared with relying on clinic-based testing alone.

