
**Cost-effectiveness analyses (CEA).** To examine the cost effectiveness of each condition under various scenarios (e.g., population prevalence/incidence, with/without follow-up for specific users, retesting intervals, purchase price), we will use mathematical models similar to those used in past CEA studies of HIV testing strategies. In CEA, a strategy is considered cost-

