effective if the gains in health justify the resources needed to implement the program. The basic element of CEA is the incremental cost-effectiveness ratio, or the difference in the total costs associated with a given testing program versus an alternative, over the difference in incremental health improvement conferred by each program, generally measured in Quality Adjusted Life Years (QALYs). While HIV testing programs can lead to increased costs because treatment can begin earlier and continue for longer, these costs can be offset by lower rates of hospitalization and treatment for opportunistic infections, and more QALYs. To evaluate Aim 3, we will calculate the total annual costs associated with providing each HBST condition (standard and eTEST), including the costs of tests, postage, sensors, web development/maintenance, counselor resources, training, and supervision. Some of these costs depend on flexible aspects of the program, including the retesting interval (3 mos., 6 mos.), follow up strategy (only positive tests versus all tests) and purchase price. As such, we will estimate the marginal intervention costs under various scenarios to compare them with similar estimates for clinic-based, rapid HIV testing programs for MSM in high-prevalence areas from the literature. Potential health gains from testing programs include: Longer life, better quality of life, reduced risk of transmission to others among those with reactive results due to earlier awareness, diagnosis, and treatment entry, and reduced future infection risk among those testing negative by linking them with PrEP and other prevention services. These also depend on outcomes for each program, like test acceptance, the number/timing of new cases detected, rates of linkage to care and treatment initiation, and rates of linkage to other prevention services among non-infected individuals. Gains conferred by these factors will be estimated using study data and available studies to compare them with existing programs. Overall, the goal of these simulations is to arrive at an estimate of the costs associated with each HBST program under various conditions per quality-adjusted life year (QALY) gained, so that they can be compared with similar estimates for clinic-based testing programs targeting similar populations. These estimates can then be used to evaluate whether providing low or no-cost HBST (with or without follow-up) can be cost effective when targeted toward certain high-incidence populations, compared with existing clinic-based approaches.

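### The cost-effectiveness steps cost only the two HBST arms and name only published clinic programmes as comparator, so no step sets Aim 3's comparison against the randomised control arm

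*Combined protocol and SAP*

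**What the plan says.** Section B.1 states Aim 3 as follows: "To assess the cost-effectiveness of the eTEST system for improving rates of HIV testing compared with clinic-based testing alone". The Overview of Research in the same section repeats it as "the cost-effectiveness of these strategies compared with relying on clinic-based testing alone", and describes the third randomised arm as "reminders for clinic-based testing only (control").

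In B.4, Planned Analyses, the cost-effectiveness text opens with a wide scope: "To examine the cost effectiveness of each condition under various scenarios". It defines the incremental cost-effectiveness ratio by its numerator, "the difference in the total costs associated with a given testing program versus an alternative", divided by the difference in health improvement, usually in QALYs.

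The working steps are narrower. On costs: "we will calculate the total annual costs associated with providing each HBST condition (standard and eTEST"), with a list that covers kits, postage, sensors, web work and counsellor time. Marginal costs are then estimated under several scenarios "to compare them with similar estimates for clinic-based, rapid HIV testing programs for MSM in high-prevalence areas from the literature". Health gains are to come from study data and other available studies, and are to be compared with existing programmes. The end product is a cost per QALY gained for each HBST programme, "so that they can be compared with similar estimates for clinic-based testing programs targeting similar populations".

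**The concern.** The trial has a concurrent randomised arm close to the comparator that Aim 3 names, but the steps do not use it on the cost side or name it anywhere as the reference. Three things are at stake.

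- **The estimand.** The plan defines an incremental ratio, but its final step sets one programme's cost per QALY beside figures published for others.
- **Comparability.** Participants have not tested for HIV in the last 12 months. If the published programmes served men with a different testing history, the contrast mixes population with programme. Randomisation would remove this problem, and the plan gives no reason for setting it aside.
- **Background testing.** Control men also test: 62% had done so in the pilot to date. Unless that baseline is subtracted, testing that would have happened anyway may be credited to HBST.

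No ratio of eTEST against standard HBST is specified either. Yet Design Considerations in B.4 treats the benefit of follow-up beyond standard HBST as something to be learned first, and the sensors and counsellors are costs that only eTEST carries.

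**Working it through.** **1. The steps side by side.** The cost-effectiveness text states no cost, QALY or ratio, so there is no figure to reproduce.

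| Element | Stated intention | Step described |
|---|---|---|
| Scope | Each condition | Costs for standard HBST and eTEST only |
| Comparator for costs | Clinic-based testing alone | Published clinic programmes |
| Comparator for gains | An alternative programme | Existing programmes; data source is the study plus other studies |
| Final output | Incremental ratio | Cost per QALY per HBST programme, beside clinic estimates |

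The control arm appears in none of the steps. The itemised costs contain no text reminders and no clinic tests.

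**2. Why two ratios do not give the increment.** Let a be the HBST programme's cost per QALY, b the clinic programme's, and k the ratio of HBST QALYs to clinic QALYs. Then

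incremental ratio = (a·k − b) / (k − 1).

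Unless a = b, this depends on k, which a comparison of a with b does not supply. If the published b is itself incremental, its baseline is that study's own and not this trial's.

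**3. Illustration of what a comparator does.** Inputs: pilot rates of any HIV test (B.1) of 96% for eTEST, 90% for standard HBST and 62% for control. These are interim rates from 73 enrolled men. Let C be the cost per man in the HBST arm concerned, and f the control cost as a share of C. The documents do not give f; I assume 0 to 0.5.

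- Uncompared cost per man tested: C/p.
- Incremental cost per additional man tested: (1 − f)C/(p − 0.62).
- Multiple (second over first): p(1 − f)/(p − 0.62).

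| Arm | p − 0.62 | Uncompared | Incremental, f = 0 | Multiple | Incremental, f = 0.5 | Multiple |
|---|---|---|---|---|---|---|
| eTEST | 0.34 | 1.04C | 2.94C | 2.82 | 1.47C | 1.41 |
| Standard HBST | 0.28 | 1.11C | 3.57C | 3.21 | 1.79C | 1.61 |

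In between, f = 0.10 gives 2.54 and 2.89, and f = 0.25 gives 2.12 and 2.41.

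**4. eTEST against standard HBST.** The pilot difference is 0.96 − 0.90 = 0.06. With s the ratio of standard cost to eTEST cost, the multiple is 0.96(1 − s)/0.06 = 16(1 − s). The documents give no s. For s = 0.5, 0.8 and 0.9 it is 8, 3.2 and 1.6.

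**The case against.** The best defence is that Aim 3 promises mathematical models under various scenarios, not a within-trial economic evaluation. Some scenarios, such as six-month retesting or follow-up of positive tests only, have no randomised counterpart, so outside inputs are unavoidable. The control arm is text reminders with a clinic list, which is itself an intervention and not a clinic testing programme. The plan also speaks of marginal costs, QALYs gained, each condition and study data, all of which leave room for control-arm outcomes on the effect side.

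Much of this stands. A literature comparator is a legitimate modelling choice, and the documents do not say that control outcomes are excluded. It does not close the gap on costs, where only two arms are listed, or on the named comparator, which is external at each step. The opening scope also conflicts with costing two arms out of three.

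A second objection is that the plan's measure is cost per QALY, not cost per man tested, and that nothing in it credits all testing to HBST. That is right. The multiples show how much a comparator can matter; they do not estimate an error in a planned result.

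A third is that a contrast of eTEST with standard HBST goes beyond Aim 3. That is also fair, but both arms are already costed and follow-up is already a scenario, so specifying it adds little work.

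**Conclusion.** The point holds as a mismatch between the aim and the described method, firmest for costs and for the named comparator. The illustrated multiples, 2.8 to 1.4 for eTEST and 3.2 to 1.6 for standard HBST, rest on small interim pilot rates and on an assumed control cost of 0% to 50% of HBST cost.

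Three stronger readings are not supported.

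- A reader might infer that Aim 3 has lost its randomised comparator altogether. The text is silent on whether the study data used for health gains include the control arm, so this cannot be said.
- A reader might infer that the published programmes served different populations. The plan specifies MSM in high-prevalence areas and similar populations. Confounding is possible, but it is not shown.
- A reader might divide 96 by 6 and infer a 16-fold understatement for eTEST against standard HBST. That takes s = 0 and charges the whole eTEST cost to a 6-point gain, although B.4, Experimental Conditions, has both arms receiving four kits at the same intervals. Only 16(1 − s), with s unknown, can be stated.

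**What to change.** Amend the cost-effectiveness text under Planned Analyses as follows.

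1. Cost the control arm: text reminders plus the clinic tests that participants report. The quarterly questionnaires already ask whether, how and where each participant tested, in every arm, and clinic records support this where available. Unit costs for clinic tests can be sought in the literature already planned. Count clinic tests in the HBST arms on the same basis.
2. Specify incremental ratios for standard HBST against control, eTEST against control, and eTEST against standard HBST. Use the randomised differences in testing, linkage and PrEP as model inputs, and say so in place of the general reference to study data.
3. Do not rely on the observed difference in diagnoses. The exploratory section expects at least 20 in total, 6 per group, and accepts that this may be too few. Derive diagnoses from testing rates and an assumed incidence, or carry their wide uncertainty through sensitivity analysis.
4. Keep the comparison with published clinic programmes as a scenario analysis.

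If the external comparator is intended as the main one, the minimum is to state this, justify it, and reconcile it with the opening promise to cover each condition.

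The cost is some extra analysis and wider uncertainty around the ratios. Recruitment, conduct and data collection do not change, and analysis is not due until Year 5.

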## Planned Analyses

Analyses will be conducted in Year 5. To evaluate Aim 1(a), we will use factorial logistic regression to test whether rates of having completed any HIV test over the 12 month study period (assessed via self-report and/or clinic records) differ by study condition. Condition, study site (and their interaction) and other relevant covariates will be entered as predictors, allowing us to explore whether each condition's effects differ by study site. To explore the effects of study condition on regular HIV testing, we will use a generalized estimating equation (GEE) for repeated, binary outcomes, specifying whether participants tested during each 3-month study period as the focal outcome. A logit link function and independent correlation structure will be specified, with study condition, site, and relevant covariates as predictors, to test whether the odds of testing differ across time period, condition, and site. GEEs are a fitting approach for studies in which correlations between repeated measures variables are to be controlled, rather than a central focus of the analysis. For all models of **HIV testing** outcomes, a covariate reflecting whether a given participant had initiated PrEP (and when, for longitudinal models) will be added to each model, since these individuals are required to test for HIV quarterly as a part of ongoing PrEP care. Doing so will allow us to estimate the effects of study arm on HIV testing among those who did not initiate PrEP. Given that we have proposed collecting 54 more participants per site (162 total) than is required to estimate our most complex model (see Model 1b in Section 3C.3.10), we believe we will be fully powered to test this model, even with a high rate of PrEP adoption. While contamination of the control group in our pilot study was rare (only one control participant reported using a HBST), we will also track **where** each participant tested (at home, in person) in quarterly surveys. If contamination is significant, we will employ methods aimed at reducing this bias, including adding indicators of contamination as covariates or bootstrapping. To evaluate Aim 1(b), we will generate variables reflecting whether participants received testing for other STIs or risk reduction counseling during each of the four 3-month intervals of the study period. Similar GEE models will be estimated for these outcomes with time period, condition, and site as predictors, to test whether the odds of receiving each service differ across these factors. To evaluate Aim 2, we will code variables indicating whether participant reports or clinic records reflect participants having consulted with a medical provider about PrEP and/or received a PrEP prescription any time across the study period. Factorial logistic regression with study site, condition, and their interaction will be entered as predictors of this outcome, to test whether the odds of having received consultation and/or a PrEP prescription differ across each of the study sites and conditions. Overall, data from those who drop out or withdraw from the study will be used in these analyses, in intent-to-treat (ITT) fashion. Similarly, we will assume values of zero for all outcomes (i.e., non-receipt of testing or services) when quarterly assessments are missing but participants are retained in the study. Depending on the degree of missing assessments, we will use multiple imputation for these values, since data from missing assessments will likely be missing not at random.

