**Power Considerations.** We used past studies and power estimation/ simulation packages in *R*, to determine the sample sizes necessary to detect significant effects in each of the models proposed in 3C.3.8. Relative risk ratios (RRs) were estimated for relevant outcomes (e.g., HIV testing, STI testing) across study conditions in our pilot data, and we used the smallest of these group differences for estimation so as to provide the most conservative estimate of required sample size. For each estimate, we assumed  $\alpha=0.05$ , an observed power of .80, and a small but constant effect (1.2) for study site on each outcome, to ensure that any differences emerging between study sites could be detected. For GEE models, we assumed quarterly measurements ( $T = 4$ ), with relatively independent relationships between repeated data ( $\Phi=0.2$ ). Table 2 summarizes the models, outcomes, parameters, and sample size estimates for each aim. For GEEs, sample size gives the estimated number of participants needed to test condition effects within each site. The sample size required to detect the most complex model with the smallest effects is 246. To account for missing data, we propose collecting 300 MSM at each site.

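### Five or six Aim 1 and 2 outcomes are tested across three arms with no primary outcome, contrast order or multiplicity rule, which puts the chance of at least one false difference at about 29–44% if eTEST is compared with each other arm at 0.05

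*Combined protocol and SAP*

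**What the plan says.** Specific Aim 1 (section B.1) asks whether eTEST gives higher rates of HIV testing and of other prevention services "compared with standard HBST and reminders for clinic-based testing among MSM in three US regions". Aim 2 adds PrEP consultation and initiation.

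Planned Analyses (section B.4) turns these aims into separate models:

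- any HIV test over 12 months (logistic regression);
- testing in each quarter (GEE);
- STI testing and risk reduction counseling (GEE for each), "to test whether the odds of receiving each service differ across these factors", the factors being time period, condition and site;
- PrEP consultation and/or prescription (logistic regression), which can be read as one variable or two.

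That makes five or six outcomes. The power paragraph introduces its settings with "For each estimate, we assumed", followed by alpha 0.05 and "an observed power of .80". No significance level is given for the analyses themselves. Nothing ranks these outcomes or says which arm comparison comes first. The only ranking in the document places new HIV cases and time to diagnosis below the rest, as exploratory or secondary.

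**The concern.** A trial offered as a definitive test of efficacy should say in advance which result decides it. Here any of ten or twelve comparisons (five or six outcomes, two comparators for eTEST) could be presented as the finding, and the choice could be made after the results are known. A nominal 5% error rate for each test then says little about the error rate of the trial's conclusion. The Overview of Research in section B.1 also plans efficacy analyses within regions, which would add further tests.

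The choice of outcome also affects how large the benefit over standard HBST appears. In the pilot, eTEST against standard HBST was 96% v 90% on any test and 92% v 54% on repeat testing. No rule says which of these measures answers the question of whether active follow-up adds value.

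**Working it through.** **The plan's own figures.** The documents state no familywise error rate. They say "The sample size required to detect the most complex model with the smallest effects is 246" and "To account for missing data, we propose collecting 300 MSM at each site". The stated margin agrees with this: 300 − 246 = 54 per site, and 54 × 3 = 162 in total. The figure 246 itself cannot be reproduced, because Table 2 is not in the available text. The power paragraph implies 300 × 3 = 900 participants, while sections B.1, B.4 and B.5 say 2000.

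**Assumptions not in the documents.** Allocation 1:1:1, which gives 2000/3 ≈ 666 or 900/3 = 300 per arm; two-sided tests; pairwise comparison of eTEST with each other arm; a common correlation between outcomes of 0 to 0.6; no true effects.

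**Step 1. Familywise error, pairwise contrasts.** For each outcome, z-statistics for eTEST v control and eTEST v standard HBST share the eTEST arm, so they correlate 0.5. Simulated trials (400,000 per row) were counted when any |z| > 1.96, and separately when any z > 1.96 in favor of eTEST.

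| Outcomes | Outcome correlation | Any false difference | False result favoring eTEST |
|---|---|---|---|
| 5 | 0 | 37.9% | 20.8% |
| 5 | 0.3 | 35.1% | 18.1% |
| 5 | 0.6 | 28.6% | 14.4% |
| 6 | 0 | 43.6% | 24.3% |
| 6 | 0.3 | 39.9% | 20.7% |
| 6 | 0.6 | 31.7% | 16.0% |

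**Step 2. Familywise error, one overall test of condition per outcome.** With independent outcomes: 1 − 0.95⁵ = 22.6% and 1 − 0.95⁶ = 26.5%.

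**Step 3. Power of a fixed-order primary test.** Power = Φ[(d − z·SE₀)/SE₁], where d is the difference in proportions, SE₀ the pooled and SE₁ the unpooled standard error. Pilot rates are from section B.1. With 300 per arm and z = 1.96:

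- eTEST v control, any test, 96% v 62%: (0.34 − 1.96 × 0.03326)/0.03022 = 9.1, power about 100%.
- eTEST v control, repeat testing, 92% v 46%: (0.46 − 1.96 × 0.03776)/0.03276 = 11.8, power about 100%.
- eTEST v standard HBST, repeat testing, 92% v 54%: (0.38 − 1.96 × 0.03625)/0.03276 = 9.4, power about 100%.
- eTEST v standard HBST, any test, 96% v 90%: (0.06 − 1.96 × 0.02083)/0.02069 = 0.93, power 82%. With 666 per arm it is 99%.

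**Step 4. Worst-case cost for secondary outcomes.** Bonferroni over 12 tests uses 0.05/12 = 0.00417, z = 2.865. For 96% v 90% (10% v 4% gives the same numbers):

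- 666 per arm: (0.06 − 2.865 × 0.01398)/0.01388 = 1.44, so power falls from 99% to 92%.
- 300 per arm: (0.06 − 2.865 × 0.02083)/0.02069 = 0.015, so power falls from 82% to 51%.

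Holm is never less powerful than Bonferroni. With one outcome taken out as primary, at most ten tests remain, so these losses are an upper bound.

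**The case against.** The strongest reply is that the documents never say each contrast will be tested at 0.05. That stands: 0.05 appears only as a power assumption, and Planned Analyses asks whether outcomes differ by condition without specifying pairwise tests. A reader might infer that every outcome and contrast is tested at 0.05. This is a natural reading of Aim 1, but an inference. With one overall test per outcome the error is still 23–27% for independent outcomes.

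A reader might also take 29–44% as the chance of a false efficacy claim. It is not: it counts differences in either direction. The chance of a false result in favor of eTEST is 14–24%. Both ranges assume no effects anywhere, which the pilot makes unlikely for HIV testing.

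A third inference would be that correction is nearly free. That fits the pooled eTEST contrasts at 666 per arm. It fails for a 12-way Bonferroni correction at the 300 per site in the power paragraph. Nor can 96% v 90% and 10% v 4% be called the smallest pilot effects. STI testing is described only as modestly higher, its rates are not in the text, and 10% v 4% is given only against control.

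It might also be said that the two pilot testing measures contradict each other. They do not, since both favor eTEST. They come from 73 participants, the repeat measure covers only the 63% who had completed Month 5, and it is not the planned quarterly GEE outcome.

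Finally, adjusting across separate aims is partly a matter of judgment, and the site interaction is already described as something to explore. None of this supplies a primary outcome or a testing order.

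**Conclusion.** The concern holds in this form: five or six Aim 1 and 2 outcomes in three arms have no primary outcome, contrast order or multiplicity rule. On the pairwise reading at two-sided 0.05, with outcome correlation 0 to 0.6 and no true effects, the chance of at least one false difference is about 29–44%, and of a false result favoring eTEST about 14–24%. On the overall-test reading with independent outcomes it is about 23–27%. All are well above 5%. The exact level depends on choices the plan leaves open, which is itself part of the gap. Power for STI testing under any correction cannot be judged from the documents.

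**What to change.** Before any analysis of outcomes by arm, add to Planned Analyses:

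1. One Aim 1(a) outcome is primary, for example the quarterly-testing GEE.
2. It is tested in fixed order at two-sided 0.05: eTEST v control, then eTEST v standard HBST only if the first succeeds.
3. Only if both succeed, Holm at 0.05 is applied to all remaining Aim 1 and 2 outcomes, including the other Aim 1(a) outcome. Without this gate, two families each held at 0.05 could reach 1 − 0.95² = 9.75%.
4. The plan states whether PrEP consultation and prescription are one outcome or two.
5. Site-level results are labeled exploratory.

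This is a change of wording, with no change to data collection. At pilot rates the first primary test has about 100% power even with 300 per arm, so the primary sequence costs almost nothing. If any HIV test were chosen instead, the second step, and hence the gate, would have 82% power at 300 per arm and 99% at 666.

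The real cost falls on secondary outcomes, at worst 99% to 92% at 666 per arm but 82% to 51% at 300. The totals of 900 and 2000 must therefore be reconciled before the rule is fixed. Labeling site-level results exploratory also means revisiting the power paragraph, which sizes the GEE models within each site.

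### The assurance that any site differences could be detected is not supported across outcomes, no condition-by-site effect size is given in the text, and the condition contrast tested alongside that interaction is not named

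*Combined protocol and SAP*

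**What the plan says.** Under Power Considerations (B.4), the sample size is set for 80% power at alpha 0.05. For sites, the calculation supposes "a small but constant effect (1.2) for study site on each outcome, to ensure that any differences emerging between study sites could be detected". The condition effects come from the pilot, and the only scale named is relative risk: "Relative risk ratios (RRs) were estimated for relevant outcomes". The same paragraph says that the GEE sample size is for condition effects within a site. It gives 246 for the most complex model and raises this to 300 per site for missing data. The Overview of Research (B.1) gives 2000 in total and 666 per metro area.

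Planned Analyses enters condition-by-site in two logistic models. For any HIV test, Aim 1(a): "Condition, study site (and their interaction) and other relevant covariates will be entered as predictors", described as a way to explore whether condition effects vary by site. For Aim 2: "Factorial logistic regression with study site, condition, and their interaction will be entered as predictors of this outcome". The GEE models name condition and site but no condition-by-site term. The Overview promises to assess "efficacy within and across regions".

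**The concern.** Entering a site effect in a power calculation does not make that effect detectable. The sentence nevertheless presents detectability of any site difference as a property of the design, for every outcome. A team relying on it could take a non-significant site or interaction test as evidence that Jackson, Los Angeles and Providence/Boston behave alike, when the test had little chance of showing otherwise.

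Two related points follow. A site effect that is the same in every arm is, on its own scale, the absence of an interaction, so it cannot support a search for condition effects that vary by site. And once the interaction is in the logistic model, the condition coefficient means different things under different codings. The plan does not say which contrast answers Aims 1(a) and 2.

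**Working it through.** **Inputs.** Alpha 0.05 (two-sided assumed); site effect 1.2; T = 4 and correlation 0.2 for the GEE (Power Considerations). Three arms, 1:1:1 assumed, so 100 per arm per site at 300 and 222 at 666. Pilot rates are from B.1, in the order eTEST/standard HBST/control. The pilot text gives no PrEP rate for standard HBST, so I set it to the control value of 4%.

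**The plan's own figure.** The 246 cannot be rebuilt without Table 2. The surrounding arithmetic agrees: 246/300 = 0.82, an allowance of 18%; 300 - 246 = 54, and 3 x 54 = 162, as Planned Analyses says.

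**1. Site effect as an odds ratio of 1.2, two sites, stratified by arm.** For an arm with rate p at one site and q at the other (odds of q = 1.2 x odds of p), v = 1/(n p(1-p)) + 1/(n q(1-q)). Then SE = (sum of 1/v over arms)^(-1/2), and power = Phi(ln 1.2/SE - 1.96) + Phi(-ln 1.2/SE - 1.96), with ln 1.2 = 0.1823.

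Example: any test, n = 222. The three 1/v are 3.90 (96%), 9.25 (90%) and 25.48 (62%), total 38.63. SE = 0.161, 0.1823/0.161 = 1.13, power 20.5%. For the GEE, the variance is multiplied by (1 + 3 x 0.2)/4 = 0.4.

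| Pilot rates | Single, 300/site | Single, 666/site | GEE, 300/site | GEE, 666/site |
|---|---|---|---|---|
| Any test 96/90/62 | 11.8% | 20.5% | 22.5% | 43.3% |
| Repeat test 92/54/46 | 16.2% | 30.2% | 33.3% | 62.5% |
| Counseling 72/15/18 | 14.6% | 26.7% | 29.4% | 56.1% |
| PrEP consultation 25/4/4 | 10.5% | 17.4% | 19.0% | 36.1% |
| PrEP start 10/4/4 | 8.5% | 12.9% | 13.9% | 25.1% |

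The pilot gives no per-quarter rates, so the GEE columns use these as stand-ins. The plan uses GEE for testing and services, not for PrEP, so the low end of the GEE range is illustrative. With one common base rate in all arms, the maximum at 666 per site is 38% (single outcome) and 75% (GEE).

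**2. Site effect as a risk ratio of 1.2.** Two-proportion power with n per site, rates p1 = p and p2 = 1.2p, and m their mean: Phi{[(p2 - p1)√n - 1.96√(2m(1-m))] / √(p1(1-p1) + p2(1-p2))}.

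| Base rate | 300/site | 666/site |
|---|---|---|
| 4% | 7% | 11% |
| 10% | 12% | 21% |
| 25% | 28% | 53% |
| 46% | 62% | 92% |
| 62% | 90.5% | 99.8% |

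Power crosses 80% at a base rate near 38% (666 per site) or 56% (300 per site). The ratio cannot hold above 1/1.2 = 83%: 1.2 x 90% = 108%, 1.2 x 92% = 110%, 1.2 x 96% = 115%.

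**3. Condition-by-site, as an illustration.** The plan gives no interaction size in its text, so I use a ratio of odds ratios of 1.2. The variance is the sum of 1/(n p(1-p)) over four cells. The most favorable pilot pair, 54 v 46 with 222 per cell, gives SE = 0.270 and power 10%, or 19% with the GEE factor. Across pilot pairs, power is 5-7% (single) and 6-11% (GEE) at 300 per site, and 6-10% and 7-19% at 666.

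**4. The condition contrast.** For 96 v 90, log OR = ln(24/9) = 0.981.
- No interaction, 666 per arm: SE 0.236, power 98.6%.
- Reference-site coefficient, 222 per arm: SE 0.409 (√3 = 1.73 times larger), power 67%.
- Average of three site-specific log ORs: SE = 0.409/√3 = 0.236, power 98.6%.
- At 300 per site, the first two become 80% and 36%.
- For 25 v 4, 96 v 62 and 90 v 62, one site of 222 per arm still gives over 99.9%.

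**The case against.** The strongest reply is that the scale of 1.2 is open and relative risk is the only scale the paragraph names. On that reading the design does well for common outcomes: 92% power at a 46% base rate and 99.8% at 62%, with 666 per site. That stands, and so does the point that Table 2 may hold scales, base rates or interaction parameters; its absence from the text is not counted against the plan. But the sentence covers each outcome and any difference. The risk-ratio reading fails at PrEP rates and is impossible in the arms at 90% or above.

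A reader might infer that the plan meant to power the interaction at 1.2. The documents do not say so: they apply 1.2 to site alone, and Aim 1(a) calls the interaction a way to explore. On a risk-ratio scale, a ratio of 1.2 reaches about 60% power at high base rates, so the figures below 20% belong to the odds-ratio illustration.

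A reader might also infer that the main condition test loses two thirds of its information. That is true only of a reference-site coefficient. The plan specifies no coding, factorial regression fits a site-averaged test equally well, and that test loses almost nothing. For the large pilot effects even one site is enough. What remains is an unnamed contrast. Finally, the plan does size its GEE for condition effects within each site; this supports within-region estimates but not a comparison of effects between regions.

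**Conclusion.** The concern holds in limited form. The assurance is wrong as written: on the odds-ratio reading no case examined reaches the planned 80% power for a site difference of 1.2, and on the risk-ratio reading only common outcomes below the ceiling do. No single power figure describes the design, because the answer depends on scale, base rate, model and the unreconciled site size (300 or 666). The text offers no basis for detecting condition-by-site differences. The risk to the condition test is conditional: 99% to 67% for 96 v 90 at 666 per site under reference-site coding, and almost nothing under a site-averaged contrast. A reader should not conclude that the trial is underpowered for its main condition comparisons; these calculations do not show that. They rest on two-sided tests, equal allocation, complete data, pilot rates holding at every site, and equal correlation of 0.2 between quarters.

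**What to change.** 1. Delete the statement that any site differences could be detected. State whether 1.2 is an odds ratio or a risk ratio, and for which base rates.
2. Reconcile 300 with 666 per site, then state the site effect and the condition-by-site effect detectable with 80% power at that size, by outcome.
3. For Aims 1(a) and 2, test condition in a model with condition and site only, or prespecify a site-averaged contrast if the interaction stays in.
4. Fit the interaction in a second model as an exploratory likelihood-ratio test. Report site-specific estimates with confidence intervals, and state that a non-significant result will not be read as equal effects across sites.

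The cost is a wording change, one extra model per outcome, and a less favorable but accurate statement of what the design can show about sites. No added participants or data are needed.
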